Proportion of patients with pneumonia. 1) Inclusion Criteria Age 18 years; 2) The time from onset to randomization was within 12 hours; 3) Anterior circulation ischemic stroke was preliminarily determined according to clinical symptoms or imaging examination: 4) Occlusion of the intracranial internal carotid artery, the M1- or M2-segment of the middle cerebral artery confirmed by CT angiography (CTA), MR angiography (MRA), or digital subtraction angiography (DSA); Baseline National Institutes of Health Stroke Scale (NIHSS)>6; 5) 6) Baseline Alberta Stroke Program Early CT Score (ASPECTS)<6: Planned treatment with endovascular therapy (EVT); Informed consent obtained from patients or their legal representatives. Intracranial hemorrhage confirmed by cranial computed tomography (CT) or **Exclusion Criteria** magnetic resonance imaging (MRI). 2) mRS score ≥ 2 before onset. 3) Pregnant or lactating women. 4) Allergic to contrast agents or glucocorticoids. 5) Participating in other clinical trials. Systolic blood pressure >185 mmHg or diastolic pressure >110 mmHg, and oral antihypertensive drugs cannot control. Genetic or acquired bleeding constitution, lack of anticoagulant factors, or oral anticoagulants and INR > 1.7. 8) Blood sugar < 2.8 mmol/L (50 mg/dl) or > 22.2 mmol/L (400 mg/dl), platelet $< 90 \times 10^{9}/L$. The artery is tortuous so that the thrombectomy device cannot reach the target vessel. 10) Bleeding history (gastrointestinal and urinary tract bleeding) in recent 1 month 11) Chronic hemodialysis and severe renal insufficiency (glomerular filtration rate < 30 ml/min or serum creatinine > 220 umol/L [2.5 mg/ dL]). 12) Life expectancy due to any advanced disease < 6 months. Follow-up is not expected to be completed. 13) Intracranial aneurysm and arteriovenous malformation. 14) Brain tumors with imaging mass effect. 15) Systemic infectious disease. **Treatments** The emergency interventional team is on call 24 hours a day, 7 days a week. Each sub-center selects patients based on the above inclusion and exclusion criteria, and assigns them to either the intravenous methylprednisolone sodium succinate + endovascular treatment group (experimental group) or the placebo (i.e., intravenous methylprednisolone sodium succinate simulator) + endovascular treatment group (control group) in a 1:1 ratio by a web-based APP on mobile phone or computer. Randomization will be stratified by participating centres permutation block size of 8. After patients agree to participate and obtain a random number, they will receive intravenous methylprednisolone sodium succinate or placebo treatment as soon as possible, preferably before the establishment of arterial access and no later than 2 hours after the completion of endovascular treatment. Relevant time points (accurate to the minute) will be recorded truthfully and accurately. The effectiveness and safety of the two treatment regimens will be observed and evaluated.

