4.4. Privacy Protection

completely stored in the hospital where they receive treatment, and laboratory test reports and other examination results will be recorded in the patients' medical records. Only the investigators, ethics committees, and food and drug administration departments of this study will be allowed to access patients' medical records. Any public reports on the results of this study will not disclose the personal identities of patients. We will make every effort to protect the privacy of patients' personal medical information within the limits allowed by law.

According to medical research ethics, apart from personal privacy information, trial data will be available for public inquiry and sharing. Inquiry and sharing will be limited to web-based electronic databases to ensure that no personal privacy information is leaked.

5. Sample Size Calculation

Based on the research results from published literature and combined with clinicians' experience, the 90-day mortality rates for the intravenous methylprednisolone sodium succinate + endovascular treatment group (experimental group) and the placebo + endovascular treatment group (control group) are estimated to be 29% and 38%, respectively. Assuming a 1:1 ratio for the sample sizes of the two groups, a two-sided α of 0.05, and a power of 80%, the estimated sample size is 856 patients. Considering an expected dropout rate of 5%, the maximum estimated sample size, calculated using PASS 15.0, is 902 patients, with 451 patients in each of the intravenous methylprednisolone sodium succinate + endovascular treatment group (experimental group) and the placebo + endovascular treatment group (control group).

6. Randomization

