8.6. Management of Residual Stenosis

Arterial ischemic stroke can be classified into thrombotic stroke, embolic stroke, and combined stroke of both. Among them, thrombosis often develops secondary to stenosis. In this study, after successful thrombectomy, if >70% stenosis is found at the site of thrombosis formation, to further prevent re-occlusion after recanalization, the surgeon will decide whether to perform emergency stent implantation and other necessary measures after 10 minutes of observation.

9. Schedule of Assessments

Each patient, after signing the informed consent form, will undergo baseline examination, randomized group treatment study, and follow-up with mRS scoring at 90 days. The trial steps and items to be evaluated at each time point are listed in Table 1.

Table 1: Trial steps and items to be evaluated at each time point.

Evaluations/ Steps	Screening Treatm period ent period		ent	Follow up period	
	12h	12h~48h	2d~discharge	90 (±7) day	
Informed consent	X				
Demographic data	X				
Medical history	X				
Pre-stroke mRS	X				
Blood pressure and heart rate	X	X	X		
NIHSS score	X	X	Xa		
ASPECTS score	X				
mRS score				X	
EQ-5D score				X	
Blood routine examination	X				
Blood biochemistry	X		X		
Coagulation function	X				
Urine pregnancy test (women of childbearing age)	X				
Head CT/MRI and CTA/MRA/DSA	X				
ECG	X				
Inclusion/exclusion criteria	X				
Randomization	X				
Study medication ^b	X	X			
DSA Endovascular treatment		X			
Head CT/MRI		X			
Treatment medication		X		X	
Intracranial hemorrhage		X			
Adverse events		X	X	X	
Complications		X	X	X	
Completion status of clinical research				X	

Note: a5-7 days or at discharge (if hospital stay is <5 days); b2mg/kg, with a maximum of 160mg, administered consecutively for 3 days.

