10.2.2. Secondary Safety Endpoints

- Proportion of patients with asymptomatic intracranial haemorrhage (aSICH) within 48 hours after EVT; 1)
- 2) The incidence of non-intracranial hemorrhage complications (including gastrointestinal bleeding, urethral bleeding, oral or nasal mucosal bleeding, and subcutaneous hematoma, etc.);
- The incidence of non-hemorrhagic serious adverse events (including cerebral hernia, pneumonia, respiratory failure, circulatory failure, stress ulcer, secondary epilepsy, urinary tract infection, sepsis, renal failure, acute coronary syndrome, venous thrombosis, and psychiatric symptoms, etc.);
- 4) Operation and device-related complications (including artery rupture, artery dissection, implant failure, stent

Release date: July 23, 2024

fracture, vascular puncture site complications, vasospasm, and device not in place, etc.);

5) Glucocorticoid-related adverse events (including insulin use in hospital, new-onset diabetes, lung infection during hospitalization, gastrointestinal bleeding within 7 days after surgery, etc.).

11. Adverse Events

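### Section 10.2.2 item 5 counts lung infection and insulin use only up to death or discharge, both of which treatment may affect; a fixed window is needed (minor, secondary safety endpoint)

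*Combined protocol and SAP*

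**What the plan says.** Item 5 of section 10.2.2 groups the glucocorticoid-related adverse events. Three of its components carry a time limit:

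- Insulin: "insulin use in hospital", with no number of days.
- Lung infection: "lung infection during hospitalization", with no number of days.
- Gastrointestinal bleeding: "gastrointestinal bleeding within 7 days after surgery", a fixed window.

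Pneumonia also appears elsewhere, without a hospital limit:

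- The synopsis has its own safety endpoint, "Proportion of patients with pneumonia", with no window. It also names pneumonia among the examples of any adverse event.
- Another item of 10.2.2 reads "The incidence of non-hemorrhagic serious adverse events (including cerebral hernia, pneumonia, respiratory failure" and so on, again with no window but restricted to serious events.

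Insulin use is not an endpoint anywhere else. Table 1 (section 9) marks adverse events in all three post-screening columns, the last being the 90-day visit ("Adverse events X X X"), and section 9.3 continues safety monitoring for 30 days beyond follow-up. Section 12.3 compares categorical outcomes by chi-square or Fisher's exact test and mentions neither time at risk nor death as a competing event.

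**The concern.** Length of stay is determined after randomisation. Note a to Table 1 provides for early leavers ("at discharge (if hospital stay is <5 days"), so stays vary. A stay ends in death or in discharge. The primary endpoint is mortality, with rates that "are estimated to be 29% and 38%, respectively" (section 5), and early neurological status and functional recovery are secondary endpoints. On the trial's own hypotheses, therefore, the period over which item 5 looks for events may differ between arms.

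With the same daily risk of infection in both arms, an arm with fewer early deaths is watched for longer and shows more infections. An arm whose patients recover and leave sooner shows fewer. The two effects pull in opposite directions, so the sign of the distortion is not known in advance. Infection is an expected harm of a glucocorticoid, and item 5 is the endpoint labelled as drug-related, so an artefact there could be taken for a drug effect or could mask one.

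**Working it through.** **The plan's own figure.** The documents give no figure for item 5. The mortality inputs come from the sample-size calculation, which reproduces: (1.960 + 0.842)² × (0.29×0.71 + 0.38×0.62) / 0.09² = 427.8, so 428 per arm and 856 in all. Then 856/0.95 = 901.05, so 902.

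**Inputs from the documents.** 90-day mortality m: 38% control, 29% drug. Patients per arm: 451.

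**Assumed inputs, because the documents give none.** First-infection hazard, equal in both arms: 0.06 per day to day 3, 0.04 to day 7, 0.02 after. Of the 90-day deaths, 70% fall in the first 14 days at a constant hazard. Survivors leave on a fixed day.

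**Death hazard:** d = -ln(1 - 0.70m)/14.
- Control: -ln(1 - 0.266)/14 = 0.0221 per day.
- Drug: -ln(1 - 0.203)/14 = 0.0162 per day.

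**Cumulative incidence.** In each interval from a to b with infection hazard h, the contribution is S(a) × h/(h+d) × [1 - exp(-(h+d)(b-a))]. S(a) is the probability of being alive and infection-free at a.

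| Interval (days) | Control | Drug |
|---|---|---|
| 0-3 | 15.95% | 16.09% |
| 3-7 | 11.08% | 11.40% |
| 7-12 | 5.50% | 5.81% |
| Total to day 7 | 27.03% | 27.49% |
| Total to day 12 | 32.53% | 33.30% |

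**Differences, drug minus control, with no true effect on infection:**

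| Window | Difference (points) |
|---|---|
| In hospital, 12-day stay in both arms | 33.30 - 32.53 = +0.77 |
| In hospital, drug-arm stay 14 days | 35.35 - 32.53 = +2.82 |
| In hospital, drug-arm stay 10 days | 31.10 - 32.53 = -1.43 |
| Fixed 7 days, discharged or not | 27.49 - 27.03 = +0.46 |

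The +0.46 left under the fixed window comes entirely from deaths.

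**Sensitivity.** A second set of assumptions uses a flat infection hazard of 0.02 to 0.06 per day, 50% to 90% of deaths within 14 days, and control survivors leaving at day 14.
- Survival alone (drug arm also leaves at day 14): +0.6 to +2.3 points.
- Drug-arm survivors leave at day 12: -1.3 to -3.6 points.
- Drug-arm survivors leave at day 10: -3.8 to -9.1 points.
- Fixed 7-day window: +0.2 to +0.8 points.

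**Scale.** At an assumed incidence of about 35% with 451 per arm, the standard error of the difference is √(2 × 0.35 × 0.65/451) = 3.2 points, so the 95% half-width is 1.96 × 3.2, about 6.2 points.

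**The case against.** The strongest reply is that pneumonia has other planned counts. The synopsis counts it with no hospital limit, serious pneumonia is counted separately in 10.2.2, and adverse events are recorded to day 90. That stands. A reader might infer from item 5 that the trial counts lung infection only while patients are in hospital, and the documents do not support that. The limit belongs to item 5 alone, and only insulin use lacks another endpoint. The other counts do not settle item 5, however: one is restricted to serious events, the others state no window, and nothing says which pneumonia count is the planned one.

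Second, size. The only part tied to the plan's figures is the survival effect. It is under 1 point in the main illustration, against a half-width of about 6 points, and the 7-day window removes only about 0.3 of it (0.77 - 0.46). The 29% and 38% are also 90-day rates, not in-hospital rates. All of this stands. The larger figures need stays that differ between arms. Note a to Table 1 shows that early discharge can happen, not that it differs by arm.

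Third, in-hospital events are documented in the chart, whereas 90-day follow-up is by outpatient visit or telephone (section 3). That is a real cost of a fixed window and a reason to keep the in-hospital count as well.

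Last, section 12.1.1 leaves derivations and methods to a plan finalised before database lock, so the matter can still be settled there.

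**Conclusion.** The point holds for item 5 of section 10.2.2 and no further. Its windows for insulin use and lung infection end at death or discharge, which treatment may affect, while the bleeding component beside them has a fixed window. Separately, the synopsis and 10.2.2 define the pneumonia count differently, and the two must be reconciled.

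On the main assumptions the distortion is +0.8 points from survival alone, and +2.8 or -1.4 points if stays differ by 2 days. Flat hazards with 14-day stays widen the survival-only range to +0.6 to +2.3. Every one of these sizes rests on assumed stays, infection rates and timing of deaths. They show that the window can bias the comparison, not that it will. A reader might go on to infer that the trial's infection results would be seriously misleading; the documents give no basis for that.

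This is a minor point on a secondary safety endpoint. The primary efficacy endpoint, the primary safety endpoint and the sample size are unaffected.

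**What to change.** 1. In item 5, state one fixed window from randomisation for lung infection and one for insulin use, for example 7 days, the length already used for gastrointestinal bleeding. Apply it to every patient, discharged or not.
2. Keep the in-hospital counts as supportive, and add a count to day 90 from the adverse events already recorded. Insulin use after discharge should be asked about specifically at that contact.
3. Show deaths without the event beside each count, as cumulative incidence with death as a competing event. This is needed because a fixed window removes the effect of discharge but not that of death.
4. Reconcile the pneumonia endpoint in the synopsis with 10.2.2, and say which count is the planned one.
5. Leave the insulin component as worded. Narrowing it to newly started insulin would be a different endpoint and would need its own reason.

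**Cost.** A short edit to 10.2.2, the synopsis and the analysis plan, with no new visit. A 7-day count captures fewer events (about 27% against 33% to day 12 on the assumed rates). Events after an early discharge depend on recall at the day-90 visit or call, about 12 weeks later.

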11.1. Definition

11.1.1. Definition of Adverse Events (AE)

AE refers to an adverse medical event that occurs after a patient or clinical trial participant receives a drug or device, but it does not necessarily have a causal relationship with the treatment.

11.1.2. Severity Determination of Adverse Events

The intensity or severity of AE is divided into four

levels according to the following criteria:

Mild: Does not affect daily activities;

Moderate: Affects the patient's daily activities;

Severe: Loss of daily activity;

Serious: Refer to SAE definition.

11.1.3. Definition of Serious Adverse Events (SAE)

SAE refers to events that occur during a clinical trial and result in: death; severe deterioration in the health of the patient, user, or others; life-threatening illness or injury; permanent impairment of body structure or bodily function; hospitalization or prolongation of existing hospitalization; medical or surgical intervention to prevent permanent impairment to body structure or bodily function, resulting in fetal distress, fetal death, or congenital anomalies/birth defects.

Note: Hospitalization that is planned in advance for pre-existing conditions or as required by the clinical trial protocol, without severe deterioration in health, is not considered an SAE.

11.2. Reporting Procedures

11.2.1. Adverse Event Reporting

Adverse events (AEs) that occur during this trial will be reported by the investigators and clinical units to the corresponding national and local regulatory authorities within the prescribed time, in accordance with national regulations. They will assist the competent authorities in investigating the AEs and take appropriate corrective and preventive measures.

The investigators shall follow up, observe, and record detailed information and outcomes of all AEs, and track patients who withdraw from the study due to AEs until the AEs are completely resolved. The investigators must determine whether the AEs are related to the investigational device and provide evidence to support this judgment.

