7.1. Implementation of Blinding

In this trial, a biostatistician generates two sets of random medication codes using a statistical software package.

The sponsor packages the medications according to the random codes, with the drug boxes labeled as "Medication for the MIRACLE Multicenter, Randomized, Double-Blind Clinical Trial of Early Combination Therapy with Methylprednisolone Sodium Succinate for Acute Large Core Infarct Recanalization." The label also indicates the drug code, random number, properties, specifications, production date, expiration date, storage conditions, and manufacturer.

The external packaging, color, and shape of the investigational drug and placebo are identical, making it impossible to distinguish between the experimental group drug and the control group drug. Grouping or treatment information is not known.

This trial uses envelopes to enclose emergency plans or/and the treatment regimens received by the subjects. This allows for unblinding in case of serious adverse reactions that require trial termination, ensuring prompt and appropriate treatment.

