7.3. Unblinding Regulations

This trial employs a two-step unblinding method. After blinded verification and data locking, the staff responsible for keeping the blinded data at the statistical center performs the first unblinding, informing the biostatistician of the group corresponding to each case number using the codes A and B. This allows for statistical analysis of all the data. When the statistical analysis is complete and the final report is ready, a second unblinding is conducted at the clinical summary meeting to announce the exact groups represented by A and B.

If during the trial, the entire blinded data is leaked or the rate of emergency envelope opening exceeds 20%, this double-blind trial will be considered invalid.

8. Treatment

The emergency interventional team is on standby 24 hours a day, 7 days a week. Each sub-center screens patients according to the above inclusion and exclusion criteria, assigning them to the experimental group and the control group in a 1:1 ratio. After randomization, patients receive intravenous injections of methylprednisolone sodium succinate or placebo (i.e., methylprednisolone sodium succinate simulator) treatment as soon as possible. Relevant time points (accurate to the minute) are recorded faithfully and

accurately, and the efficacy and safety of the two treatment regimens are observed and evaluated.

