11.3. Prediction and Countermeasures of Adverse Events

All adverse events (AEs) that occur during the trial must be recorded truthfully in the AE form. Investigators should provide targeted treatment for AEs and conduct follow-up visits until the symptoms disappear or stabilize. For cases of serious adverse events (SAEs), investigators should immediately take necessary treatment measures upon learning of them to protect the safety of patients. Common AEs that may occur during interventional procedures include, but are not limited to:

1) Thromboembolic events

Possible causes include inadequate anticoagulation or incomplete anticoagulation, insufficient antiplatelet aggregation therapy or aspirin resistance, and the absence of continuous perfusion in the coaxial system. Reasonable and standardized anticoagulation and antiplatelet aggregation should be performed. If embolism occurs in important blood vessels, it should be managed by a professional doctor based on the patient's condition.

2) Cerebrovascular spasm

Cerebrovascular spasm can be caused by subarachnoid hemorrhage or irritation from intravascular catheters or guidewires. If cerebrovascular spasm occurs, symptomatic treatment should be provided by a professional doctor based on the patient's condition.

3) Acute occlusion

Possible causes include endothelial injury, platelet aggregation, and thrombosis, which usually occur within 30 minutes after balloon angioplasty or are related to endothelial avulsion.

Preventive measures: Antiplatelet agents such as aspirin or clopidogrel can effectively reduce acute thrombosis events.

Treatment measures: In case of acute occlusion, reasonable treatment should be immediately provided based on the cause of the occlusion.

4) Thrombosis and plaque dislodgment

These are mainly caused by the crushing and dislodgment of plaques during stent deployment or balloon dilation, and sometimes also due to thrombosis induced by catheters or guidewires. The use of cerebral protection devices and intraoperative anticoagulation are basic measures to prevent such events.

5) Vascular rupture

This type of complication can directly lead to patient death. When performing stent angioplasty in certain areas, it is advisable to choose an inner stent that is slightly smaller than the diameter of the target vessel. In case of vascular rupture, immediate symptomatic treatment should be provided by a professional doctor.

6) Cerebral hyperperfusion syndrome

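### The only explicit adverse event causality instruction names an investigational device, although the trial randomises a drug and tests no device

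*Combined protocol and SAP*

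**What the plan says.** Section 11.2.1 (Adverse Event Reporting) requires follow-up and recording of all adverse events and then sets the causality rule: "The investigators must determine whether the AEs are related to the investigational device and provide evidence to support this judgment".

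The randomised product is described differently elsewhere. The opening of Section 8 (Treatment) states that after randomisation "patients receive intravenous injections of methylprednisolone sodium succinate or placebo (i.e., methylprednisolone sodium succinate simulator) treatment as soon as possible". Section 7.1 calls the product a drug: "The external packaging, color, and shape of the investigational drug and placebo are identical". Section 8.1 gives both arms endovascular treatment by any of several techniques.

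Section 11.1.1 defines an adverse event broadly: "AE refers to an adverse medical event that occurs after a patient or clinical trial participant receives a drug or device". It adds that a causal link is not needed, but it sets no procedure for judging one.

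Section 10.2.2 lists five secondary safety endpoints. The fourth is "Operation and device-related complications". The fifth is "Glucocorticoid-related adverse events (including insulin use in hospital, new-onset diabetes, lung infection during hospitalization, gastrointestinal bleeding within 7 days after surgery, etc".

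**The concern.** The instruction is a binding duty on investigators, in an operative section, and it points at the wrong object. Followed literally, it asks whether an event was caused by a stent retriever, catheter or stent. It does not ask whether the event was caused by the steroid or placebo that the trial compares.

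The error is not certain to correct itself at the sites. Endovascular devices are used in every planned procedure, so the word has a natural literal meaning here. One centre may read it as the thrombectomy equipment and another may silently substitute the study drug, and the two would then record answers to different questions in one field. Under the literal reading, the field describes an exposure common to both arms and says nothing about the drug.

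What is at stake is the quality of individual case assessment: whether a given event, such as a gastrointestinal bleed or an infection, was thought attributable to the blinded study drug. Section 13.2 sets no stopping criterion for safety, so the DSMB works by judgment, and a correctly aimed causality assessment would be useful background for it.

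**Working it through.** No arithmetic applies and the plan gives no figure to reproduce. The check is a reading of the available text for any instruction on cause or relatedness.

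1. **What is under test.** Sections 7.1, 8 and 8.1: methylprednisolone or matching placebo, with endovascular treatment in both arms. No device is randomised or named as investigational.

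2. **Explicit causality instructions.** One, in 11.2.1, and it names a device. Instructions that require each adverse event to be judged against methylprednisolone or the blinded study drug: none.

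3. **Could another section supply the missing rule?**
   - 11.1.1 mentions both drugs and devices, but only to define an adverse event.
   - 11.2.2 sets time limits for serious events (16 hours to the lead unit, 24 hours to the ethics committee) with no causality step.
   - 11.3 describes six expected events linked to the procedure or to recanalisation. It is introduced as a non-exhaustive list for interventional procedures, so it neither supplies a drug-causality rule nor shows that drug events were overlooked.
   - 4.3 attaches follow-up duties to terminations due to an adverse reaction and to serious events related to the study. Sections 7.1, 9.2 and 9.3 also speak of adverse reactions. These imply some judgment of relatedness, but none says how it is made or against what.
   - 10.2.2 separates drug-type from device-type harm by endpoint. The four events named under the glucocorticoid item can be counted by type without a causality call.

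4. **What depends on the wording?**
   - *Between-arm comparison of safety events.* Section 12 plans no analysis by relatedness, and comparing event counts by randomised arm needs none. Not affected.
   - *Reporting of serious events.* 11.2.2 covers any serious adverse event, whatever its cause. Not affected.
   - *DSMB.* Section 13.2 has adverse events sent to the DSMB chair, with a data report after every 100 patients complete follow-up, and no condition on causality. Not affected.
   - *Case-level causality for the study drug.* Nothing in the available text requires it to be recorded. Affected.

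5. **Extent.** The instruction covers every adverse event in 902 planned patients, 451 of them allocated to the steroid. That is the reach of the rule and does not measure harm. The documents give no adverse event rates from which to estimate the number of events.

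**The case against.** The strongest reply is that this is a wording slip with little practical effect. The document mixes drug and device language in several places (11.1.1, 13.1 and 17.4), investigators know they are giving a steroid or placebo, and the randomised comparison is better evidence of drug harm than any individual attribution. Most of this stands, and it is why the point is minor. It does not make the instruction right, and the use of real devices in this trial is what allows the slip to be read literally.

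A second reply is that the adverse event form, the CRF with its filling instructions and the DSMB charter were not available, nor was the body of Section 19, which the contents list shows as including the monitoring committee. Any of these may ask about the study drug. That also stands. If the form does ask, the protocol contradicts it and still needs correcting.

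A reader might go further and infer that no event will be assessed for relation to methylprednisolone, or that the DSMB will lack what it needs. The documents do not support either. Sections 4.3, 9.2 and 10.2.2 imply some relatedness judgments, and reporting to the lead unit and the DSMB is unconditional. A reader might also infer from the open ending of the glucocorticoid endpoint that membership turns on judged causality. Items 2 to 4 of the same list are open-ended too, and nothing says that further events enter by attribution. That is a separate matter of endpoint definition, which a causality field would not settle.

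**Conclusion.** The point holds in limited form. The one explicit causality rule names an object that the trial does not test, and no available text requires each adverse event to be judged against the blinded study drug, although 10.2.2 itself distinguishes drug-type from device-type harm. The consequence is confined to case-level causality assessment. The randomised safety comparison, the reporting of serious events and the flow of adverse events to the DSMB stand as written.

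Section 11.2.1 also defers to national regulations on reporting. Whether those call for a drug-causality judgment is not stated in the documents, and this conclusion does not rely on it. It does rest on the assumption that no unseen form or charter already supplies the rule. If one does, what remains is an inconsistency between documents. Either way this is a low-severity correction, worth making because it is cheap and concerns patient safety.

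**What to change.** In Section 11.2.1, replace the reference to the investigational device with the blinded study drug (methylprednisolone or placebo). Keep relation to the endovascular procedure or its devices as a second, separate judgment. Both are made without knowledge of allocation, consistent with Section 7. Make the adverse event form match, so that the two answers are recorded separately.

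The cost is one sentence of protocol wording, up to two fields on the adverse event form (fewer if the form already has them), and a short extra judgment per event. Because 11.2.1 asks for evidence behind each judgment, the extra work is small but not nil. No change to the sample size, the endpoints or the planned analyses is needed.
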